### Per Protocol Analysis Set

The per protocol (PP) analysis set includes all ITT subjects who does not meet one or more of the following criteria:

- Deviations from the inclusion and exclusion criteria:
  - Inclusion criteria not fulfilled (#02): No histologically and/or cytologically confirmed diagnosis of SCCHN
  - Inclusion criteria not fulfilled (#03): No recurrent and/or metastatic SCCHN not suitable for local therapy
  - Inclusion criteria not fulfilled (#06): ECOG performance status of 0 or 1
  - Exclusion criteria fulfilled (ex#01): Prior systemic chemotherapy, except if given as part of multimodal treatment for locally advanced disease which was completed within 6 months before trial entry. (as per Protocol Amendment)
  - Exclusion criteria fulfilled (ex#03): Previous treatment with monoclonal antibody or signal transduction inhibitors targeting EGFR.
  - Exclusion criteria fulfilled (ex#04): Nasopharyngeal carcinoma.
- Randomization error:
  - Incorrect treatment group allocation, different to assignment at randomization
  - Subject randomized but did not receive any trial treatment
- Use of prohibited medication:
  - Additional concurrent chronic systemic immune treatment, chemotherapy, radiotherapy (with exceptions), hormone treatment for treatment of cancer (with exceptions), traditional Chinese medication with approval for use as anticancer treatment or any other investigational agent

- Availability of measurement of the primary endpoint:
  - No evaluable post-baseline tumor assessment (as per IRC) is available

If the Per Protocol analysis set includes at least 90% of subjects in the ITT analysis set, additional efficacy analyses on the Per Protocol analysis set and baseline analysis (including demographics) on PP/safety set will be omitted as the differences in the results based upon these two analysis sets are expected to be negligible.

| Analyses                       | Intent-to-Treat Analysis Set | Per Protocol Analysis Set | Safety Analysis Set |
|--------------------------------|------------------------------|---------------------------|---------------------|
| Demographics                   | ✓                            | ✓                         | ✓                   |
| Baseline Assessments           | ✓                            | ✓                         |                     |
| Past and Concomitant Therapies | ✓                            |                           |                     |

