### 12.2.2 Reasons Leading to the Exclusion from an Analysis Set

Subjects who meet at least one criteria described in section 10.2 will be excluded from the PP. For these subjects, each criteria will be summarized and listed;

- Frequency table per criteria

Listing of each criteria.

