### 16.1 Primary Endpoint Analyses

#### 16.1.1 Primary Analysis of Progression Free Survival (PFS)

Analysis Set

- ITT, PP (as sensitivity analysis if less than 90% of ITT)

The primary endpoint of this trial is PFS time as assessed by independent radiology read. IRC will perform *radiology* and *clinical* reviews as described in the IRC Charter. The results of the *radiology* review will be used for the primary analysis.

The PFS time by IRC is defined as the duration (in months) from the date of randomization until first observation of PD (based on imaging as assessed by IRC), or death due to any cause when death occurs within 60 days after the last tumor assessment or the randomization (whichever is later).

Any subject with neither assessment of tumor progression, nor death date within 60 days after last tumor assessment or randomization will be censored on the date of last tumor assessment or randomization. A subject who has not received trial treatment and for whom no date of progression or death is known will be censored on the date of randomization (Day 1) or date of last tumor assessment, whichever comes later. The following censoring rules will be applied.

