**Censoring Rules**

| Situation                       |  | Date of event / censoring                           | Censoring |
|---------------------------------|--|---|-----------|
| Radiological PD (RECIST 1.1)    |  | Date of PD  | No        |
| No radiological PD (RECIST 1.1) | If death within 60 days after last tumor response assessment or the randomization (whichever is later) | Date of death (CRF)                                 | No        |
|                                 | If death not within 60 days after last tumor response assessment / No death                            | Date of last tumor response assessment within trial | Yes       |

Special cases which overrule general rules:

|  |   |                       |     |
|--|---|-----------------------|-----|
| No tumor assessment at baseline  | Death within 60 days after date of randomization                | Date of death         | No  |
|  | Death not within 60 days after date of randomization / No death | Date of randomization | Yes |
| No tumor assessment after start of treatment and no radiological PD (RECIST 1.1) | Death within 60 days after date of randomization                | Date of death         | No  |
|  | Death not within 60 days after date of randomization / No death | Date of randomization | Yes |

The last tumor assessment date is defined as the last available and evaluable tumor assessment performed prior to the cut-off date (or prior to EoS, i.e. subjects lost to follow-up or who withdraw consent). If no evaluable tumor assessment is available, this date will be the randomization date.

Imputation methods for estimating missing data:

- For imputing missing parts of dates for the efficacy analyses (except OS) the missing day in a date will be imputed as the 15th of the month, if month and year is documented. If the imputation is earlier than the date of randomization, the day of randomization is taken. In all other cases missing or incomplete dates will not be imputed.

- For imputing missing day of death date, if month and year is available, the day will be imputed by 15, unless this results in a date not later as a date the subject is known to be alive. In that case the date of death will be imputed by the last date known to be alive + 1.

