- Events: Radiological PD based on existing lesions (progressive disease reported for target and/or non-target lesions) / Radiological PD based on new lesions (new lesion(s) is/are reported) / Radiological PD based on existing and new lesions (both progressive disease reported for target and/or non-target lesions and new lesion(s) are reported) / Death within 60 days
- Censoring: Death not within 60 days / Censored at randomization / Lost to follow-up or withdraw consent / Due to data cut-off

Subjects will be considered as “censored at randomization” in case they have no tumor assessment at baseline and no tumor assessment after start of treatment and no radiological PD or death.

They will be considered as censored due to “Lost to follow-up/withdraw consent” in case they have no PD or death before they are lost to follow-up/withdraw consent.

They will be considered as censored “due to cut-off” in case they have no PD or death before the trial data cut-off.

A listing will display information on event and censoring including the following:

- Subject identification number,
- Treatment arm
- Randomization Date
- Last tumor assessment date before cut-off date
- Death date
- Progression date (IRC)
- PFS (IRC): Censoring Flag (Yes/No)/ Description of the Event/Censoring/ PFS (months)

A scatter plot will be produced to compare planned (y-axis) and actual (x-axis) relative day of tumor assessments by treatment arm (2 colors will be used to clearly identify treatment groups). The planned day for EOEA visit will be assigned as the planned day for the last available efficacy assessment visit.

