### 16.1.2 PFS Sensitivity Analyses

To assess the robustness of the primary analysis, the following analyses can be conducted:

- Per-protocol analysis: the same analysis as described above Section 16.1.1 will be repeated on PP analysis set only if PP analysis set includes less than 90% of the ITT analysis set.
- The same analysis as described above Section 16.1.1 will be repeated using results of the *clinical* review from IRC, corresponding listing will also be produced.
- The same analysis as described above Section 16.1.1 will be repeated considering all death as event.
- The same analysis as described above Section 16.1.1 will be repeated considering all death and start of new anti-cancer treatment as event.
- To address the bias due to different times of assessment of disease progression caused by different treatment schedules, the same analysis as described above Section 16.1.1 will be repeated considering date of planned imaging visits instead of date of actual imaging visits. If an event is observed between two planned visits, it will be assigned to the previous one. The planned day for EOEA visit will be assigned as the planned day for the last available efficacy assessment visit.
- The same analysis as described above Section 16.1.1 will be repeated excluding subjects who met the inclusion criteria 3 as defined in protocol version 1.0 (17 November 2014) but who do not meet the updated inclusion criteria 3 as defined in protocol version 2.0 (20 April 2016). Please refer to [Appendix 2](#) for the details for inclusion criteria 3.
- The same analysis as described above Section 16.1.1 will be repeated based on the stratification factors based on eCRF data instead of IWRS data.

Results of PFS primary and sensitivity analyses (hazard ratio and 95%CI) will be displayed using a forest plot.

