## 17.2 Deaths, Other Serious Adverse Events, and Other Significant Adverse Events

### 17.2.1 Deaths

All deaths, deaths within 30 days after last dose of trial treatment (cetuximab, cisplatin, carboplatin, or 5-FU), deaths within 60 days after first dose of trial treatment as well as the primary reason for death, will be tabulated based on information from the “Report on Death” eCRF page:

- Any subject who died and primary reason for death
  - Progressive disease and/or disease related condition
  - Related to trial treatment(s)
    - Cetuximab
    - Cisplatin
    - Carboplatin
    - 5-FU
  - Event unrelated to trial treatment

- Unknown
- Subjects who died within 30 days after last dose of treatment and primary reason for death
  - Progressive disease and/or disease related condition
  - Related to trial treatment(s)
    - Cetuximab
    - Cisplatin
    - Carboplatin
    - 5-FU
  - Event unrelated to trial treatment
  - Unknown
- Subjects who died within 60 days after first dose of treatment and primary reason for death
  - Progressive disease and/or disease related condition
  - Related to trial treatment(s)
    - Cetuximab
    - Cisplatin
    - Carboplatin
    - 5-FU
  - Event unrelated to trial treatment
  - Unknown

In addition, date and cause of death will be provided in individual subject data listing together with selected dosing information (date of first / last administration, separately for cetuximab, cisplatin, carboplatin, and 5-FU).

This listing will also include:

- Data from “Report on Death” eCRF page
- Flag for death within 30 days after last dose of trial treatment
- Flag for death within 60 days after first dose of trial treatment

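### The per-protocol rule on missing post-baseline IRC scans removes early deaths that the primary endpoint counts as PFS events

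*SAP*

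**What the plan says.** **PP membership.** SAP 10.2 lists the PP exclusions. Under a heading about whether the primary endpoint could be measured, the only entry is "No evaluable post-baseline tumor assessment (as per IRC) is available". Section 12.2.2 applies the list without exceptions: "Subjects who meet at least one criteria described in section 10.2 will be excluded from the PP".

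**Primary endpoint.** SAP 16.1.1 defines PFS by IRC as time to first IRC progression "or death due to any cause when death occurs within 60 days after the last tumor assessment or the randomization (whichever is later". The censoring table has a special row for subjects with "No tumor assessment after start of treatment and no radiological PD (RECIST 1.1". In that row a death within 60 days of randomization is an event on the date of death, and everyone else is censored on the date of randomization. Last assessment means the last available and evaluable one, and "If no evaluable tumor assessment is available, this date will be the randomization date".

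**Use of PP.** SAP 16.1.2 lists PP first among the PFS sensitivity analyses. The primary analysis "will be repeated on PP analysis set only if PP analysis set includes less than 90% of the ITT analysis set".

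**The concern.** For a subject who dies on, say, day 30 before any evaluable scan, the endpoint has been measured: it is a PFS event on day 30. The PP rule treats that subject as unmeasured and removes the event, which is selection on a component of the outcome after randomization. Death before the week-6 scan is not non-adherence either, so the exclusion does not serve the usual purpose of a PP set.

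Two things follow. A difference between the PP and ITT hazard ratios would partly reflect deleted events and could be misread as an effect of protocol deviations. Early deaths also count towards the exclusions that decide whether the PP analysis is run at all.

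**Working it through.** **1. The plan's own figures.** The success threshold is reproduced from the 46% PFS risk reduction in Protocol 3.7.2: 1 − 0.46/2 = 0.77. It is applied to ITT. For the 90% rule with 240 subjects, 216/240 = 90.0% (PP omitted) and 215/240 = 89.6% (PP run), so PP runs at 25 or more exclusions.

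**2. Who the criterion removes.** Reading evaluable in 16.1.1 as IRC-evaluable:

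| Subject with no evaluable post-baseline IRC scan | Status in SAP 16.1.1 | Information in the Cox model |
|---|---|---|
| Dies within 60 days of randomization | Event at death | Yes |
| Dies later, or no death | Censored at randomization | None |

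An IRC progression is itself an evaluable assessment, so no progressor is removed. With the plus-one duration rule in SAP 11, censoring at randomization gives a time of 1 day. Such subjects could share a risk set only with a death on the day of randomization itself, and the criterion removes that death too.

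This was checked in simulated trials of 240 subjects (2:1, six strata, stratified Cox model with discrete ties as in 16.1.1; 10 scenarios of 150 trials). Removing the subjects censored at randomization changed the hazard ratio by 0 in every trial. Removing early deaths did change it: with 5% early deaths in each arm, the geometric mean moved from 0.781 to 0.766.

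**3. How many early deaths.** The documents give no early-death rate. The nearest anchor is the pair of OS medians in Protocol 3.7.2 (10.1 and 7.4 months). Assume a constant hazard, and that every death by day 42 is unscanned:

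- Cetuximab arm: 160 × (1 − exp(−ln 2 × (42/30.4375)/10.1)) = 160 × 0.0904 = 14.5
- Control arm: 80 × (1 − exp(−ln 2 × (42/30.4375)/7.4)) = 80 × 0.1212 = 9.7

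That is about 14 vs 10. Half is 7 vs 5. A quarter is 3.6 and 2.4, or 4 vs 2 after rounding.

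**4. Effect on the PP hazard ratio.** Assumptions: 160 vs 80 subjects; control median PFS 3.3 months (Protocol 3.7.2); hazard ratio 0.77 among subjects who reach the first scan; scans every 42 ± 3 days; early deaths uniform on days 3 to 41; 12-month accrual; cut at 144 events. A further 25 subjects are excluded at random for other reasons, so that PP runs with or without the fix. The model is an unstratified Cox model with Efron ties, with 800 trials per row except the 4 vs 2 row, which comes from separate runs of the same design.

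| Unscanned early deaths, cetuximab vs control | ITT | PP, early deaths kept | PP as written | Mean paired difference |
|---|---|---|---|---|
| 14 vs 10 | 0.754 | 0.755 | 0.769 | +0.019 |
| 7 vs 5 | 0.765 | 0.764 | 0.771 | +0.009 |
| 4 vs 3 | 0.775 | 0.777 | 0.783 | +0.007 |
| 4 vs 2 | – | – | – | about −0.007 |
| 3 vs 2 | 0.776 | 0.777 | 0.779 | +0.003 |

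The hazard ratios are geometric means and the last column averages within-trial differences, so the columns do not subtract exactly. The Monte Carlo standard error of the difference is at most 0.0014 in the 800-trial rows.

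At 14 vs 10, PP as written has 108 events, standard error 0.203 and a 95% CI of about 0.52 to 1.14. With the deaths kept it has 129 events, standard error 0.185 and a CI of about 0.53 to 1.08.

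Splits not derived from the medians give other values. Equal rates in the arms give −0.015 (8 vs 4) and −0.029 (16 vs 8). Strong imbalances give +0.046 (8 vs 8) and −0.094 (16 vs 4).

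**5. Effect on whether PP runs.** With 24, 12 or 6 unscanned early deaths and no other subjects without a scan, PP as written needs 25 − 24 = 1, 25 − 12 = 13 or 25 − 6 = 19 other exclusions. With early deaths kept it needs 25.

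**The case against.** Requiring an evaluable IRC scan is a prespecified, labelled choice, and it conflicts with no other part of the plan. ITT is primary and keeps every such death, and another sensitivity analysis in 16.1.2 counts all deaths as events. PP is conditional and carries no decision rule. The outputs also expose the exclusions: 12.2.2 tabulates and lists each PP criterion, the PFS event table in 16.1.1 has a row for "Death within 60 days", and 17.2.1 tabulates "deaths within 60 days after first dose of trial treatment". The PP result with these deaths restored could be rebuilt from the listings.

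All of that stands and keeps the point minor. It does not remove it: a reader sees how many subjects were dropped, but no planned analysis gives the PP hazard ratio with their events kept.

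Three stronger readings are tempting, and the documents do not support them.

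- **That early deaths are certainly the only removed subjects who matter.** The PP criterion specifies the IRC; the 16.1.1 definition of the last evaluable assessment does not. If an investigator-evaluable scan can set that date, a subject whose scans the IRC could not evaluate may carry follow-up, or have an event within 60 days of that scan, and is also removed.
- **That the rule favours one arm.** The sign follows the arm split: 4 vs 3 and 4 vs 2 differ by one control-arm death and point in opposite directions.
- **That the trial's positive or negative call is at risk.** The 0.77 criterion is applied to ITT, which this rule does not touch.

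**Conclusion.** The point holds and is minor. As written, the PP set drops subjects whose PFS event was observed, under a rule meant for subjects whose endpoint was not. That follows directly from SAP 10.2 and 16.1.1 and needs no simulation. That early deaths are the only channel to the PP hazard ratio depends on reading evaluable as IRC-evaluable in 16.1.1.

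At the counts derived from the OS medians, the shift is about 0.02 or less, small against a PP confidence interval running from about 0.5 to 1.1. This size is illustrative and not a bound. It assumes constant hazard and medians from another trial. It treats all deaths to day 42 as unscanned, although symptoms may prompt earlier imaging (Protocol 5.1). It also leaves out deaths on days 43 to 60 in subjects whose week-6 scan was missed or not evaluable. The larger shifts need early-death splits for which the documents give no basis.

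**What to change.** In SAP 10.2, narrow the criterion to: "No evaluable post-baseline tumor assessment (as per IRC) is available" *and no death within 60 days after randomization*. Add the narrowed criterion to Appendix 1 for completeness. Never-treated subjects remain excluded under their own criterion. It would also help to state in 16.1.1 whether evaluable means IRC-evaluable when the last assessment date is set.

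The main cost is fewer exclusions, so PP reaches 90% of ITT, and is omitted, somewhat more often. This happens whenever the total is 25 or more as written but below 25 once early deaths are kept; a reader then has ITT only. PP membership also comes to depend partly on death, which affects PP counts and baseline tables.

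Deleting the criterion altogether is simpler and, on the IRC-evaluable reading, gave the same hazard ratio in every simulated trial. Narrowing is preferable: it fits the heading of the rule, and because living subjects without a scan still count as exclusions, PP is dropped less often than under deletion. ITT, data collection and the decision rule do not change.

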### Specific subgroups

The following subgroups are considered of interest to comparatively explore the treatment effect for the definition of subgroups, data as documented in the eCRF will be taken.

- Age: <65 years versus  $\geq 65$  years
- Sex: Male versus Female
- Baseline ECOG performance status: 0 versus 1
- Primary tumor site: oral cavity versus oropharynx versus hypopharynx versus larynx versus others. The location of the tumor as reported on the “Disease history” eCRF page according to the International Classification of Diseases for Oncology (ICD-O) and the locations are grouped using guidance of the medical advisor.
- Time from initial SCCHN diagnosis: < median versus  $\geq$  median
- Histology: well/moderately versus poorly differentiated
- Extent of disease at trial entry: nonmetastatic recurrent (date of first occurrence of recurrent disease is available and date of first occurrence of metastatic disease is Not applicable) versus nonrecurrent metastatic (date of first occurrence of recurrent disease is Not applicable and date of first occurrence of metastatic disease is available) versus metastatic including recurrent (both dates of recurrent disease and date of first occurrence of metastatic disease are available)
- Prior antitumor therapy:
  - Any: yes versus no;
  - Prior neoadjuvant/induction: yes versus no;

- Prior radiotherapy: yes versus no;
- Prior radiochemotherapy: yes versus no;
- Prior surgery (excluding biopsy): yes versus no;
- Prior platinum-containing treatment for SCCHN: yes versus no.

A summary for the number of subjects in each subgroup will be produced. The analysis of individual subgroups will be done in a case there are enough observations in each subgroup (i.e. more than 10 subjects in any treatment group). If there are more than 2 options within a subgroup and less than 10 subjects in one of the options this option may be pooled with the closest option. The final decision on the pooling of the subgroups will be taken during the data review meeting prior to the database lock for the main analysis.

## 11 General Specifications for Statistical Analyses

This is a bridging trial. The hypothesis test will not be done and P-values will not be provided, unless otherwise specified. If CIs are to be calculated, these will be 2-sided with a confidence probability of 95%, unless otherwise specified.

### Data handling after cut-off date:

Data after cut-off do not undergo the cleaning process. The only exception is the date of death on “Death” eCRF page.

Generally, data obtained after the cut-off will not be displayed in any listings or used for summary statistics, e.g., laboratory values of samples taken after data cut-off, AE with onset date after data cutoff, etc. will not be included in any analysis or listing.

The cut-off will be implemented at SDTM level.

### Pooling of centers

In order to provide overall estimates of the treatment effect, data will be pooled across centers. The factor center will not be considered in statistical models or for subgroup analyses.

### Presentation of continuous and qualitative variables:

Continuous variables will be summarized using descriptive statistics, i.e.

- number of subjects (N), number of subjects with non-missing values
- mean, standard deviation (Sd)
- median, 25th Percentile - 75th Percentile (Q1-Q3),
- minimum and maximum,

Qualitative variables will be summarized by counts and percentages.

Unless otherwise stated the calculation of proportions will be based on the number of subjects in the analysis set of interest. Therefore counts of missing observations will be included in the denominator and presented as a separate category.

